Data on Intervention Process and Quality Assurance. Data will be collected by RAs and IEs, who will be trained in completing all questionnaires (see human subjects section for training information). Study personnel will instruct participants how to accurately respond to each questionnaire and will ensure data quality by reviewing each document for response errors and omissions. For telephone-based assessments, an assessment guide will be provided to increase reliability and validity of responses. All IEs will be blinded to participant randomization and will remind participants not to reveal any information about study interventions during assessment interviews. Study providers will not be involved in outcome data-collection and will be blind to IE assessments. Under the supervision of the PI, all IEs will be trained to administer questionnaires in a standardized manner. IEs will undergo rigorous training and calibration for all study measures. Fidelity Review The first two APT cases assigned to each clinician will be closely supervised and rated for adherence to the protocol and clinican competency by a clinician investigator; if needed, close supervision will continue for additional cases until ratings of 6 or higher (¿good¿ on a 0-8 scale) are achieved. A random 10% of the APT sessions will be monitored by [name]. If clinician adherence or competence falls below 6 for 2 consecutive tapes: ¿ Provider will receive additional supervision ¿ Supervisor will listen to all sessions until the appropriate rating is achieved for 2 consecutive sessions ¿ If provider is unable to attain integrity rating within a reasonable period of time, supervisor will decide on best course of action (eg. additional training, etc.) The first two EUPC cases assigned to each clinician will also be closely supervised and rated by a clinician investigator for adherence to the protocol. Close supervision will continue for additional cases as needed. A random 10% of the EUPC sessions will be monitored by [name]. [name] will conduct a similar review of baseline and follow-up (3, 6, and 12 month) telephone assessments by the IE for quality assurance.

Additional measures of treatment fidelity will describe the extent to which participants understand and use the skills during and after the intervention. First, during each session, providers will assess caregivers; level of understanding, using targeted questions at key points (see Appendix). These questions will be used as checkpoints to determine whether to proceed to the next session or provide additional teaching. A second measure will assess between-session use of skills. At the beginning of each session, providers will record the caregiver; sevel of participation in skills training by documenting the number of home practice assignments completed. Finally, providers will inquire about caregivers; interactions with health providers and document the caregiver; sreported use of specific provider-patient communication techniques taught in the first session.

Section H: Potential Risks/Discomforts

H1. Potential Risks/Discomforts

Describe and assess any potential risks/discomforts; (physical, psychological, social, legal, or other) and assess the likelihood and seriousness of such risks:

The potential risks foreseen generally relate to psychological discomfort that may be associated with the assessment and/or treatment process of the study. Participants may experience mild distress related to answering personal questions and/or mental fatigue from responding to multiple questions at one time. In addition, there is a limited risk of loss of privacy due to the nature of the questions. The intervention and usual care groups of this study are not expected to create any significant risk for participants. Participants will be informed about available alternative treatments including the use of additional medical treatment (where possible), and/or no treatment. In summary, the therapeutic risks are viewed as minimal as are the research risks.

H2. Data and safety monitoring plan

Do the study activities impart greater than minimal risk to subjects? No

H3. Coordination of information among sites for multi-site research

Is the BCM Principal Investigator acting as the SPONSOR-INVESTIGATOR for this multi-site research?

No or Not Applicable

Is BCM the COORDINATING CENTER for this multi-site research?

No or Not Applicable

Section I: Potential Benefits

Describe potential benefit(s) to be gained by the individual subject as a result of participating in the planned work.

Subjects may benefit from being better able to manage their pain. They may also be less likely to become aggressive.

Caregivers will learn how to better manage pain and distress and will learn to better communicate with persons with dementia. Although this is particularly true in the intervention group, those in the control group will also receive substantial educational information. Primary care providers will learn of patients; pain and depression level and therefore may be better to manage these symptoms. Given that the risks from the intervention and research assessments are minimal, we gauge the risk-benefit profile to be positive.

Describe potential benefit(s) to society of the planned work.

The current treatment of persons with dementia and aggression continues to be antipsychotic medications, which have limited efficacy and substantial adverse consequences. If this intervention is efficacious, it will provide an urgently needed alternative to current treatment. In addition, the paradigm of prevention in mental health is of growing importance. Since the risks of this proposal are minimal, the balance of risks to potential knowledge gained is very favorable.

Do anticipated benefits outweigh potential risks? Discuss the risk-to-benefit ratio.

Given that the risks of this largely educational intervention are minimal, the risk to benefit ration is positive. Patients may benefit from better management of their pain and less development of aggression, caregivers may benefit from gaining knowledge on how to better manage their care recipients who have dementia, and providers may benefit from learning more about how to address pain in persons with dementia

Section J: Consent Procedures

J1. Waiver of Consent

Will any portion of this research require a waiver of consent and authorization? Yes

Please describe the portion of the research for which a waiver is required. (Example: chart review to determine subject eligibility)

The research team will partner with participating sites to identify PWD through partial HIPAA-waiver-approved, database-generated lists of patients meeting geographical and selected ICD-9 diagnostic codes from the 046, 290, 291, 292, 294, 331 and 333 series (or corresponding ICD-10 codes). We have tried directly recruiting patients through newsletters, fliers, and through primary care doctor referral on numerous occasions without success. Initial access to the PHI is necessary to identify potentially eligible patients. Given our strict eligibility criteria, it would be impossible to recruit our targeted sample of patients w/out first limiting recruitment to dementia patients who could then be approached to evaluate for pain/pain-related symptoms.

Explain why the research and the use or disclosure of protected health information involves no more than minimal risk (including privacy risks) to the individuals.

All PHI will be kept secure and not shared. Only the study team will be able to see research records, questionnaires, and other identifying information. All information will be stored in a locked file cabinet in a locked storage room at the MEDVAMC. We will store information collected on a secure computer server behind the MEDVAMC firewall. This means that the information will be in a computer that no one outside the VA/ BCM can get into. A number will be assigned to each patient and caregiver, which will be kept separate from all identifying information, except for a password-protected master list stored on a secure server behind the MEDVAMC firewall.

Explain why the waiver will not adversely affect the privacy rights and the welfare of the research subjects.

PHI will be combined with information from other people in the study. We will write about the combined information and not about any person individually. We will not share any records unless the law requires us to. PHI will not be reused or disclosed to or shared with any other person or entity, except as required by law, for authorized oversight of the research study, or for other research for which the use or disclosure of the PHI would be permitted under the privacy rule.

Explain why the research could not practicably be conducted without the waiver and could not practicably be conducted without access to and use of the protected health information.

The research could not practicably be conducted without the waiver without access to and use of PHI because the scientific validity would be compromised if the investigators did not have access to the database. In order for the results of the study to be valid, the PI needs to be sure that the participants are appropriately selected for the study. In past studies, we have tried to recruit through other means such as through healthcare providers or advertisements, but these have not worked in this population of older adults with dementia and their caregivers. We have not been able to recruit enough subjects, and those subjects that we did recruit were not representative of the general population of persons with dementia and their caregivers. Recruiting through these traditional methods has resulted in recruiting psychologically, cognitively, and physically healthier patients (and caregivers); those that are less likely to benefit from the intervention.

Describe how an adequate plan exists in order to protect identifiers from improper use and disclosure.

PHI will not be reused or disclosed to or shared with any other person or entity, except as required by law, for authorized oversight of the research study, or for other research for which the use or disclosure of the PHI would be permitted under the Privacy Rule.

Describe how an adequate plan exists in order to destroy identifiers at the earliest opportunity consistent with conduct of the research, unless there is a health or research justification for retaining the identifiers or such retention is otherwise required by law.

Per VA policy, all research data collected, including identifiers, for this research study will be destroyed six years from the date the research study is closed.

Describe how adequate written assurances exist in order to ensure that the PHI will not be reused or disclosed to (shared with) any other person or entity, except as required by law, for authorized oversight of the research study, or for other research for which the use or disclosure of the PHI would be permitted under the Privacy Rule.

This Waiver of Consent is for obtaining database lists of patients diagnosed with dementia and their contact information. Subjects who are found to be interested and eligible will be asked to sign a written consent form that contains a statement that PHI will not be reused of disclosed to any other person or entity, except as required by law, for authorized oversight of the research study, or for other research for which the use or disclosure of the PHI would be permitted under the Privacy Rule.

Information from health records such as diagnoses, progress notes, medications, lab or radiology findings, etc.

Yes

Specific information concerning alcohol abuse:

No

Specific information concerning drug abuse:

No

Specific information concerning sickle cell anemia:

No

Specific information concerning HIV:

No

Specific information concerning psychiatry notes:

No

Demographic information (name, D.O.B., age, gender, race, etc.):

۷۵۹

Full Social Security #:

Νo

Partial Social Security # (Last four digits):

No

Billing or financial records:

No

Photographs, videotapes, and/or audiotapes of you:

No

Other:

Yes, as described: medical record numbers

Will additional pertinent information be provided to subjects after participation?

No

If No, explain why providing subjects additional pertinent information after participation is not appropriate.

This is an educational intervention and patients and caregivers will be receiving substantial information during the study. Providing additional information after the study is not likely to be useful to them.

J1a. Waiver of requirement for written documentation of Consent

Will this research require a waiver of the requirement for written documentation of informed consent?

Yes

Explain how the research involves no more than minimal risk to the participants, and the specifics demonstrating that the research does not involve procedures for which written consent is normally required outside of the research context.

A home-based intervention was chosen for this study for several reasons. It may be difficult for some patients to travel to the study-site due to dementia-related cognitive/behavioral and physical factors, and other physical factors (such as pain). In addition, work schedules and the demands of caregiving may make travel to to the study-site difficult for the caregiver. In order to reduce this potential barrier and increase generalizability, all study visits will be conducted in the patient's home or via telephone. In addition, it is felt that the home-environment will be more conducive to active participation and learning

for both patients and caregivers.

Subjects will first be screened for eligibility by telephone using a telephone script (attached in Section S). Verbal consent to conduct the telephone screening and use the information collected as part of the research will be obtained before any other questions are asked. A trained research assistant (RA) will administer the 15-minute telephone screen to the caregiver and PWD. Caregivers will be asked a series of questions to assess level of PWD cognitive and functional impairment (FAST caregiver interview); presence of an eligible caregiver; and history of aggression, clinically significant pain or pain-related features, such as depression or caregiver/patient relationship problems. PWD will be asked to complete the Mental Impairment Screen, telephone version (MIS-T) to collect further data regarding cognitive impairment and will also answer questions about their current level of pain, depression, and relationship with caregiver. These questions are minimally invasive and would not require written informed consent outside of a research setting.

We feel it is necessary to conduct the screening phone call prior to written informed consent for the following reasons:

- 1) It would be impracticable to conduct home visits to obtain written informed consent for all potentially eligible subjects prior to screening due to limited study resources.
- 2) We feel it would be overly burdensome to ask to visit a patient's home without first assessing eligibility.

We plan to use the information collected on the screening telephone call as research data for the following reasons: 1) We will use the information gathered to determine the reasons potential subjects did not want to participate in the study or did not qualify for the study, to aid in the design of future research targeting this population.

2) Some of the questions asked at screening are also needed to characterize participants that enroll in the study. To reduce study burden, we will not repeat these questions after written informed consent is obtained.

If a subject is found to be eligible based on telephone screening, a trained RA will visit the subject's home to obtain written informed consent as soon as possible.

J2. Consent Procedures

Who will recruit subjects for this study?

PΙ

PI's staff

Describe how research population will be identified, recruitment procedures, any waiting period between informing the prospective participant and obtaining consent, steps taken to minimize the possibility of coercion or undue influence and consent procedures in detail.

Our patient identification and recruitment procedures are based on our prior studies of PWD. The key initial criterion for study eligibility for patients is having a dementia diagnosis. The research team will partner with participating sites through 3 recruitment mechanisms to identify PWD: (1) direct provider referral and (2) participant self-referral, (3) partial HIPAA-waiver-approved, database-generated lists of patients meeting geographical and selected ICD-9 codes from the 046, 290, 291, 292, 294, 331 and 333 series (or corresponding ICD-10 codes). We have tried directly recruiting patients through newsletters, fliers, and through primary care doctor referral on numerous occasions without success. Initial access to the PHI is necessary to identify potentially eligible patients. Given our strict eligibility criteria, it would be impossible to recruit our targeted sample of patients w/out first limiting recruitment to dementia patients who could then be approached to evaluate for pain/pain-related symptoms. A waiver of consent for database review for subject identification is attached in section S. [name] in BCM Neurology and [name] in BCM Geriatrics, along with [name] at Kelsey-Seybold, will be sharing the names, addresses, and phone numbers of their patients who meet the basic eligibility study criteria with [name] and his study staff. All data will be sent to the coordinating center (VA) for storage. Data will be stored on VA servers located at the Michael E. Debakey VA Medical Center and in locked filing cabinets in a locked filing room located at HSR&D Center of Excellence Nabisco Building [name], Storage Room 121. See Section K for further explanation of Confidentiality.

PWD identified through direct or database methods will receive a letter from the research team written at 6th-grade reading level to inform the PWD and caregiver that study staff will contact them the following week, unless they request not to be contacted by calling a toll-free number. PWD and caregivers will also be mailed response cards and the Philadelphia Geriatric Pain Intensity Scale. PWD who do not opt-out, but are not reached by phone may receive a second opt-out letter after contact information is re-verified with the referring provider.

We will attend the clinics of our clinical partners if needed to explain the study in person to any patients referred. We will collect the names and contact information of patients who are interested and schedule them for telephone screening.

Fact Sheets and flyers will be posted at dementia-specific adult day care centers in the Houston area. The flyers will specify that the PWD must be a patient of one of our clinical partners (see flyer attached in Section S). Patients and their caregivers can contact study staff to schedule a telephone screening. These fact sheets and flyers will also be distributed at community events such as the annual Alzheimer's Update at the Museum of Natural Science.

Periodically, [name], a nurse practitioner with Kelsey-Seybold Department of Neurology, or other qualified personnel will give a 45 minute talk on Coping with Dementia at the main Kelsey-Seybold Clinic at [name] The Kelsey

Research Foundation will invite active patients of Kelsey-Seybold Clinics who have been diagnosed with dementia and their caregivers to the talk. The IRB approved APT Study Fact Sheet and Flyer will be available at the talk, and study staff will be on hand to answer questions about the study. A private room will be reserved for patients who wish to screen for the study after the talk. Patients may also schedule a telephone screening for a later date.

Due to space limitations, see additional text attached in Section S.

Are foreign language consent forms required for this protocol?

No

J3. Privacy and Intrusiveness

Will the research involve observation or intrusion in situations where the subjects would normally have an expectation of privacy?

No

J4. Children

Will children be enrolled in the research?

No

J5. Neonates

Will non-viable neonates or neonates of uncertain viability be involved in research?

Nο

J6. Consent Capacity - Adults who lack capacity

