Executive Function (EF) and Self-Neglect (SN): Individuals who SN often suffer from dementia, depression, and pain, all associated with ED. Additionally, SN is associated with impaired social networks and refusal of care. Prior research indicates that, when self-neglecters refuse interventions of unpaid caregivers, there is progressive decline in personal, functional and environmental domains. Secondary Aims have been added to further understand the relationship of ED with psychosocial outcomes and refusal of care. Although the APT intervention is primarily directed to the caregiver, participation of the PWD in weekly homework is critical. Better understanding the relationship of these variables will help to inform later analyses. The CLOX Drawing Test will be administered to a subset of 100 consecutively enrolled subjects at baseline. It is a two part test (CLOX 1 and CLOX 2) to measure EF and global cognition. CLOX 1 is a more direct measure of EF. CLOX 1 consists of instructing the subject to draw a clock and insert the time of 1:45 using hands and numbers in a clock. Scores range from 0 to 15. A score of 10 or below on CLOX 1 indicates executive impairment. The CLOX has high inter-rater reliability estimates (CLOX 1, Pearson, s r = 0.94, CLOX 2, Pearson, s r = 0.93; both p < 0.001). The CLOX also has a high internal consistency (Cronbach; s alpha = 0.82). After adjusting for age and education level, the Executive Interview and Mini-Mental Status Examination strongly predicted CLOX 1 scores [F (4,82) = 50.7, p < 0.001; R2 = 0.71]. Refusal of care will be measured by clinician assessment at each weekly session with the following two questions: ¿¿How many weeks did the PWD participate in weekly sessions with the therapist?¿, and ¿How many weeks did the PWD participate in assigned homework?; Responses to each question range from 0-7 and will be summed and divided by the total number of sessions the caregiver participated in to determine the PWD; s rate of engagement in the intervention.

Section D: Purpose and Objectives

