In our prior and currently funded grants, we recruit patients using methods similar to those described in this proposal to identify PWD with clinically significant pain. To determine the number of patients available for this study, we asked our clinical partners to provide the number of PWD, using dementia ICD-IX codes and restricting to patients within 40 miles not living in a long-term care facility. We identified 1273 patients. Based on our prior studies, an estimated 60% of patients will meet the criterion for clinically significant pain, resulting in 764 existing eligible patients; broadening inclusion criteria to include pain-related features will result in even more eligible patients. On the basis of our prior recruitment data, we predict excluding approximately 30% of patients due to severe dementia, history of aggression, or lack of eligible caregiver. Thus, we estimate that 535 will meet all selection criteria. In our current APT study, we have had a consent rate of 80-90%. To conservatively estimate, an 80% consent rate results in 428 patients.

One-hundred consecutively enrolled subjects will be asked to do the CLOX Drawing Test at baseline to achieve our secondary objectives. This will give adequate power to detect significant differences of small to medium magnitude in outcomes between those with and without executive function (ED). Given an N of 100 and an alpha of 0.05, there is 97% power to detect a medium effect (F2 = 0.15) and 80% power to detect an effect size for ED (over and above two covariates) as small as F2 = 0.08.

Expected Recruitment Efforts and Minimization of Attrition. In our current VA Study and prior studies, we were able to enroll 6-8 dyads per month. In the VA study and others that we completed with PWD and their caregivers, attrition is about 10%; therefore, we plan to recruit 220 dyads, 6 patients per month over 37 months. We expect we will need to contact approximately 300 dyads using our partial HIPPA Waiver in order to enroll 220 dyads in the study.

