Secondary Hypotheses 3: PWD who screen positive for ED will report significantly higher rates of pain (Philadelphia Geriatric Pain Intensity Scale), caregiver-patient related problems (Mutuality Scale), depression (30-item Geriatric Depression Scale) and behavior problems (Revised Memory and Behavior Checklist). Differences between those with and without ED in 1) pain, 2) mutuality, 3) depression, and 4) behavior problems will be evaluated with a series of multiple

linear regression models. Four models will be conducted, one for each outcome, with ED as the primary predictor and gender and caregiver relationship as covariates.

Secondary Hypotheses 4: PWD who screen positive for ED will have significantly lower engagement in intervention than PWD who do not screen positive for ED. An additional linear regression model will be conducted to test for differences between those with and without ED in engagement (Aim 2).

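### Hypotheses 3 and 4 test executive dysfunction only as a yes/no flag although the 0–15 CLOX 1 score is recorded; using the score would normally gain power at no data cost.

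*Combined protocol and SAP*

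**What the plan says.** Section C (Executive Function and Self-Neglect) introduces the CLOX drawing test and calls CLOX 1 the more direct measure of executive function. On scoring it says "Scores range from 0 to 15" and "A score of 10 or below on CLOX 1 indicates executive impairment".

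Section D sets the secondary objectives: to examine how ED relates to pain, caregiver–patient problems, depression and behaviour problems, and how ED is associated with engagement in APT.

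In the data analysis plan, Secondary Hypothesis 3 is that "PWD who screen positive for ED will report significantly higher rates of pain", and likewise for the other three outcomes. It is tested by four linear regressions with ED as the main predictor and two covariates (gender and caregiver relationship). Secondary Hypothesis 4 makes the same screen-positive comparison for engagement, in one further linear regression. The cut of 10 is not repeated there, but it is the only one the protocol gives and is the natural reading of a positive screen.

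Section G1 sets the sample: "One-hundred consecutively enrolled subjects will be asked to do the CLOX Drawing Test at baseline to achieve our secondary objectives". It claims "adequate power to detect significant differences of small to medium magnitude in outcomes between those with and without executive function (ED"). Two figures support this. For the smaller effect, f² = 0.08, the plan gives 80% power, with ED tested on top of two covariates. For the larger one it says "Given an N of 100 and an alpha of 0.05, there is 97% power to detect a medium effect (F2 = 0.15").

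**The concern.** A 16-level score is collected and then reduced to two categories in every analysis that uses it. The stated objectives concern relationships and association, which the score can address in the same regressions. If the outcomes change gradually with executive function, the flag ignores all variation within each category, and power falls for no saving in data or burden.

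The population may make this worse. Section F1 requires mild-to-moderate dementia in everyone, plus pain, depression or relationship difficulty. Section C says of people who self-neglect (SN): "Individuals who SN often suffer from dementia, depression, and pain, all associated with ED". A sample in which most people score 10 or below is therefore plausible, and the ED-negative group could be small. The plan states no expected split and no minimum group size, and f² by itself does not show the split.

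At stake is the chance that the two ED hypotheses give a usable answer. The randomised comparison of APT with EU-PC is not affected.

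**Working it through.** **Inputs.** From Section C: score 0–15, cut at 10 or below. From Section G1: N = 100, alpha 0.05, f² = 0.15 and 0.08, one tested predictor plus two covariates. From Section F1: 1:1 allocation. Assumed, because the documents do not say: a two-sided test, the ED split, and the shape of the CLOX 1 distribution.

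**1. The plan's own power.** Noncentral F test with 1 and 100 − 3 − 1 = 96 df and noncentrality f² × N.
- f² = 0.15: noncentrality 15, power 96.95% (stated 97%).
- f² = 0.08: noncentrality 8, power 79.96% (stated 80%).

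Both figures reproduce.

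**2. Information kept by the flag.** For a normal score cut so that a share p is ED-positive, with a linear relation, the fraction of R² kept is φ(z_p)² / [p(1 − p)].
- p = 0.5: 0.3989² / 0.25 = 0.637
- p = 0.8: 0.2800² / 0.16 = 0.490
- p = 0.9: 0.1755² / 0.09 = 0.342

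**3. Power with the flag when the score has f² = 0.08.** The score's R² is 0.08 / 1.08 = 0.0741. Multiply by the fraction kept, then convert back with f² = R² / (1 − R²).

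| Split (ED+ : ED−) | R² kept | f² of flag | Power, N = 100 |
|---|---|---|---|
| score itself | 0.0741 | 0.0800 | 80% |
| 50:50 | 0.0472 | 0.0495 | 59.6% |
| 80:20 | 0.0363 | 0.0377 | 48.5% |
| 90:10 | 0.0253 | 0.0260 | 35.8% |

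**4. Sensitivity to shape.** The loss is one minus the squared correlation between a 0–15 score and the 10-or-below flag, still with a linear relation.
- Uniform: 35%
- Left-skewed example: 30%
- U-shaped examples: 26% to 31%
- Two-cluster example: 17%
- Truncated normals, over a range of means and SDs: 32% to 92%

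If the outcome really steps at 10, the flag is the right predictor and there is no loss.

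**5. f² as a group difference.** For a two-group predictor f² = p(1 − p)d², so d = √[f² / (p(1 − p))]. This needs the split but no assumption about the score's shape. For f² = 0.08:
- 50:50: √(0.08 / 0.25) = 0.57 SD
- 80:20: √(0.08 / 0.16) = 0.71 SD
- 90:10: √(0.08 / 0.09) = 0.94 SD

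Conversely, a 0.5 SD difference has f² = 0.25 × p(1 − p), that is 0.0625, 0.0400 and 0.0225. Power at N = 100 is 70%, 51% and 32%.

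**6. Hypothesis 4.** Section D ties engagement to APT, and Section C measures it by participation in therapist sessions and homework. Under 1:1 allocation about half of the 100 contribute, roughly 50. Assuming the same three-predictor model (46 df), power is 76% at f² = 0.15 and 50% at f² = 0.08, and 80% power needs f² of about 0.16. These figures apply to any single predictor, before dichotomising. If the score has f² = 0.08 under the assumptions of step 2, the flag has 34%, 27% and 20% at the three splits. At 90:10 about five of the 50 would be ED-negative.

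**The case against.** **The power statement is right.** Section G1 defines f² = 0.08 as the effect of ED itself over two covariates, and that reproduces. A reader might infer from the 60%, 49% and 36% that the plan overstated its power. It did not: those figures describe what the flag achieves if the score's effect is f² = 0.08. They compare two analyses and correct no stated number. This stands.

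**Small to medium is defensible on the f² scale.** The plan calls 0.15 medium, and 0.08 lies below it. That stands too. But the sentence describes differences between two groups, and there the reader needs the split. Even the most favourable one gives more than half an SD.

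**A loss of at least a third is not a floor.** It is one only for a roughly normal score with a linear relation. The documents give no CLOX 1 mean, SD or shape, and other bounded shapes lose less. This stands and limits the claim.

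**A very small ED-negative group is not shown.** The Section C sentence concerns people who self-neglect and states associations, not prevalence. Relationship difficulty alone suffices for entry. Section F1 excludes FAST above 6 and anyone unable to complete the telephone memory or pain screens. An uneven split is plausible, no more.

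**The cut is prespecified, and the hypotheses ask about screen-positive people.** True: this is not a data-driven cut, and a slope answers a somewhat different question. But Section D frames the aim as relationships and association, and nothing in the documents claims a threshold at 10 for these outcomes. Keeping the contrast as a companion preserves the clinical question.

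**Conclusion.** The concern holds as a cheap improvement to secondary, non-randomised analyses. The plan tests ED only as a flag, although the score is recorded and fits the stated objective. With a roughly normal score and a linear relation, the flag gives up about 36% of the information at an even split, 51% at 80:20 and 66% at 90:10. The splits are assumptions, the loss may be smaller for other shapes, and it disappears under a true threshold at 10. So neither a guaranteed loss of a third nor a tiny comparison group should be read into the documents.

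Two points do not depend on the score's shape. The power statement, correct in f² units, leaves out the split that a reader needs to interpret it as a group difference. And its N of 100 fits Hypothesis 3 only: Hypothesis 4 rests on about 50 people, under 1:1 allocation and the Section D reading that engagement means engagement in APT.

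**What to change.** 1. In the four Hypothesis 3 models and the Hypothesis 4 model, make the CLOX 1 score (0–15) the predictor that is tested. Prespecify a linearity check.
2. Report the 10-or-below contrast alongside as a companion, with the number in each group.
3. In Section G1, either tie the power figures to the score or give the detectable group difference in SD units with the assumed ED split.
4. State Hypothesis 4 power separately at about n = 50.

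The cost is wording in the analysis plan and Section G1, with no new data or visits. The downside is that the main result becomes a slope per CLOX 1 point, which is less immediate than a screen-positive contrast, and the wording of the two hypotheses has to change to match.
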